*Note: Also excluded are renally impaired patients receiving an average daily dose of simvastatin 40 mg with eGFR below <45 mL/min/1.73 m².*
- *Body mass index (BMI) ≥50 kg/m²*
- *Concomitant use of simvastatin at average daily doses greater than 40 mg.*
- *Concomitant use of a PCSK9 inhibitor (Praluent® [alirocumab] or Repatha® [evolocumab]) at Week -2 (Visit S1) or prior use of a PCSK9 inhibitor within the past 4 weeks of Week -2 (Visit S1) will be excluded from this study.*  
*Note: Patients are allowed to initiate a PCSK9 inhibitor as adjunctive therapy at Week 24 if the*

*LDL-C threshold criteria have been met as described in Section 11.1.6.3.5.*

- Recent (within 3 months prior to the screening visit [Week -2 (Visit S1)] or between screening and randomization visits) MI, unstable angina leading to hospitalization, uncontrolled, symptomatic cardiac arrhythmia (or medication for an arrhythmia that was started or dose changed within 3 months of screening), CABG, PCI, carotid surgery or stenting, cerebrovascular accident, transient ischemic attack (TIA), endovascular procedure or surgical intervention for peripheral vascular disease or plans to undergo a major surgical or interventional procedure (eg, PCI, CABG, carotid or peripheral revascularization). Patients with implantable pacemakers or automatic implantable cardioverter defibrillators may be considered if deemed by the Investigator to be stable for the previous 3 months.
- Uncontrolled hypertension, defined as sitting systolic blood pressure (SBP)  $\geq 160$  mmHg and diastolic blood pressure (DBP)  $\geq 100$  mmHg after sitting quietly for 5 minutes. Note: If the initial blood pressure (BP) values meet or exceed the specified level, an additional BP assessment may be completed. If the systolic or the diastolic values continue to meet or exceed the threshold, the patient may not continue screening. However, at the discretion of the Investigator, the screening period may be extended up to 2 weeks to allow for a repeat qualifying BP assessment following adjustment of BP medication(s), provided that the patient has been on a stable dose of the BP medication for a minimum of 2 weeks prior to randomization and the repeat BP measurements do not meet the exclusion criteria
- Hemoglobin A1C (HbA1C)  $\geq 10\%$  at Week -2 (Visit S1)

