7. Uncontrolled hypertension, defined as sitting systolic blood pressure (SBP)  $\geq 160 \text{ mmHg}$  and diastolic blood pressure (DBP)  $\geq 100 \text{ mmHg}$  after sitting quietly for 5 minutes. Note: If the initial blood pressure (BP) values meet or exceed the specified level, an additional BP assessment may be completed. If the systolic or the diastolic values continue to meet or exceed the threshold, the patient may not continue screening. However, at the discretion of the Investigator, the screening period may be extended up to 2 weeks to allow for a repeat qualifying BP assessment following adjustment of BP medication(s), provided that the patient has been on a stable dose of the BP medication for a minimum of 2 weeks prior to randomization and the repeat BP measurements do not meet the exclusion criteria
8. Hemoglobin A1C (HbA1C)  $\geq 10\%$  at Week -2 (Visit S1)
9. Uncontrolled hypothyroidism, including thyroid-stimulating hormone (TSH)  $>1.5 \times$  the upper limit of normal (ULN) at Week -2 (Visit S1). Patients stabilized on thyroid replacement therapy for at least 6 weeks prior to randomization are allowed.

10. Liver disease or dysfunction, including:

- Positive serology for hepatitis B surface antigen (HBsAg) and/or hepatitis C antibodies (HCV-AB) at Week -2 (Visit S1); or
- Alanine aminotransferase (ALT), aspartate aminotransferase (AST)  $\geq 2 \times$  ULN, and/or total bilirubin (TB)  $\geq 1.2 \times$  ULN at Week -2 (Visit S1).

*Note: If HCV-AB is positive, a reflex HCV RNA will be performed to rule out active disease. Patients without active disease may be enrolled in the study.*

Note: At the discretion of the investigator, the screening period may be extended up to 2 weeks for a single repeat of ALT, AST, and/or TB. For those patients who have a repeat ALT, AST, and/or TB, the repeat value will be used to determine eligibility.

*If TB  $\geq 1.2 \times$  ULN, a reflex indirect (unconjugated) bilirubin will be obtained and if consistent with Gilbert's disease, the patient may be enrolled in the study.*

11. Gastrointestinal conditions or procedures (including weight loss surgery; eg, Lap-Band® or gastric bypass) that may affect drug absorption
12. Hematologic or coagulation disorders or a hemoglobin (Hgb) level  $< 10.0$  g/dL (100 g/L) at Week -2 (Visit S1)

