#### 10.2.1. Screening Week -2 (Visit S1; Days -16 to -4)

The screening period will begin with a screening visit that will occur 2 weeks prior to randomization. Visit S1 will allow the Investigator to assess the patient's preliminary eligibility. After the patient provides written informed consent (see Section 10.1), the patient will undergo the following assessments and procedures at Visit S1:

- Demographics
- Clinically relevant medical history, including assessment of HeFH status and ASCVD
- Concomitant and prohibited medication review
- Height (cm), weight (kg), BMI
- Vital signs
- Clinical laboratory evaluations:
  - Hematology, blood chemistry, coagulation, and urinalysis
  - Basic fasting lipids (TC, calculated LDL-C, HDL-C, non-HDL-C, and TG)
  - HbA1C
  - TSH
  - *FSH (in appropriate female patients)*
  - Serum pregnancy test (on appropriate female patients)

- Serology (including HBsAg, HCV)
- Review of all inclusion/exclusion criteria that can be assessed at this time
- Conduct diet and exercise counseling
- Contact IWRS to register the patient

Patients who meet all enrollment criteria that can be assessed at Visit S1 will be instructed to continue their therapy(s) for lipid regulation and to maintain consistent diet and exercise patterns throughout the study. Patients who fail to meet any entry criterion that can be assessed at Visit S1 are considered to be screen failures and are not required to return for additional visits (although a patient can be seen at any time for safety reasons).

Note:

- An optional visit approximately 1 week later MAY be completed if patient fails to meet a lipid entry criterion. If this optional visit is completed, the mean of lipid values from both visits will be used to determine eligibility.
- *An optional visit between Visits S1 and T1 may be scheduled to collect screening fasting labs in the event that the patient arrives at Visit S1 in a nonfasted state.*
- An optional visit between Visits S1 and T1 may be completed if the patient's DBP and/or SBP meet the exclusion criteria levels. Patients may randomize after blood pressure medications have been adjusted, they have been on stable doses of blood pressure medications for at least 2 weeks, and the repeat blood pressure values (DBP and/or SBP) no longer meet exclusionary values.

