NOTE: For patients who withdraw from IMP treatment, but consent to be followed for safety assessments and return to clinic for these visit, the visits will occur according to the protocol schedule. Safety assessments should include clinical safety and basic lipid laboratories (except for apoB and hs-CRP), adverse events, PE, vital signs, and ECGs. For patients who withdraw from IMP treatment, but consent to be followed for safety assessments by phone, the telephone contacts will occur according the protocol schedule with information regarding current health status and to collect information on AEs (eg, recent procedures, hospitalizations, and if the patient has died, the cause of death). If a patient does not provide consent to be followed for safety assessments per the protocol (either by returning to clinic or by phone), Visit T7 will be considered the EOS/Early Withdrawal from study and no further visits will be scheduled.

 An optional visit approximately 1 week later MAY be completed if patient fails to meet a lipid entry criterion. If this optional visit is completed, the mean of lipid values from both visits will be used to determine eligibility.

 An optional visit between Visits S1 and T1 may be completed if the patient's DBP and/or SBP meet the exclusion criteria levels. Patients may randomize after blood pressure medications have been adjusted, the patients have been on stable doses of blood pressure medications for at least 2 weeks, and the repeat blood pressure values (DBP and/or SBP) do not meet exclusionary values. An optional visit between Visit S1 and T1 may be completed to determine eligibility if the patient's eGFR, ALT, AST, and/or TB meet exclusion criteria levels. If this optional visit is completed, the repeated value will be used to determine eligibility.

 All procedures will be completed for all patients at either End of Study (EOS) if completing the study or early withdrawal.

 Body weight will be measured in the morning while fasting, using consistent scales, after voiding, and without shoes and outerwear (eg, coats).

 Single 12-lead ECG will be collected prior to any blood sample collection.

 Vital signs will include DBP, SBP, and HR and will be collected prior to any blood sample collection. Patient will rest for 5 minutes prior to assessments

 Serology for HBsAg, HCV

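### Exclusion criterion 7 joins its systolic and diastolic limits with 'and', although the surrounding text shows that either high value was meant to exclude

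*Protocol*

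**What the plan says.** Protocol 7.2, criterion 7, begins "Uncontrolled hypertension, defined as sitting systolic blood pressure (SBP", gives 160 mmHg or higher as the systolic limit, and adds the diastolic limit of 100 mmHg or higher with a plain 'and'. The exclusion list in the synopsis uses the same connective: "mmHg and diastolic blood pressure (DBP".

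The note attached to the criterion has three steps.

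- First reading: "If the initial blood pressure (BP) values meet or exceed the specified level, an additional BP assessment may be completed".
- Additional assessment: "If the systolic or the diastolic values continue to meet or exceed the threshold, the patient may not continue screening".
- After adjustment of blood pressure medication and a stable period, the patient may qualify if "the repeat BP measurements do not meet the exclusion criteria".

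Protocol 10.2.1 describes an optional visit between screening and randomization that "may be completed if the patient's DBP and/or SBP meet the exclusion criteria levels". It lets the patient proceed once "the repeat blood pressure values (DBP and/or SBP) no longer meet exclusionary values". Footnote 2 of the schedule of events (Protocol Appendix 1, and again SAP Appendix 1) has nearly the same release wording: "the repeat blood pressure values (DBP and/or SBP) do not meet exclusionary values".

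All of this is current text, not amendment history.

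**The concern.** A definition that joins two limits with 'and' is met only when both are reached. A patient with a markedly raised systolic pressure and a diastolic just under 100, or the reverse, falls outside it. The remaining text treats one high value as enough. The sentence that defines the exclusion therefore disagrees with the sentences that explain how to apply it.

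Nothing else in Protocol 7.2 covers the gap. None of the other 20 numbered criteria sets a blood pressure limit, so criterion 7 is the only place where such a patient would be stopped. The population has HeFH and/or ASCVD and is enrolled as being at high cardiovascular risk. About 125 sites apply the rule. A site that works from the definition and a site that works from the note could decide differently about the same patient.

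**Working it through.** The plan states no figure on this point, and no power or sample size calculation depends on it. The check is a comparison of two rules on example readings.

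Inputs: SBP limit 160 mmHg, DBP limit 100 mmHg (Protocol 7.2, criterion 7). Rule A is the definition: excluded if SBP ≥160 and DBP ≥100. Rule B is the either-value wording of the note and of Protocol 10.2.1: excluded if SBP ≥160 or DBP ≥100.

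| Reading (mmHg) | SBP ≥160 | DBP ≥100 | Rule A (definition) | Rule B (either value) |
|---|---|---|---|---|
| 165/105 | yes | yes | excluded | excluded |
| 185/92 | yes | no | not excluded | excluded |
| 150/105 | no | yes | not excluded | excluded |
| 150/92 | no | no | not excluded | not excluded |

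The rules part exactly where one value is high. The readings and the rows are illustrations and say nothing about how often such patients present.

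Next, the three steps of the note.

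1. First reading. The definition gives Rule A. The trigger for the additional assessment refers only to values reaching the specified level and does not say whether one or both are needed. Protocol 10.2.1 offers its optional visit when DBP and/or SBP is at an exclusionary level, which makes sense only if one value can be exclusionary alone.
2. Additional assessment. The note applies Rule B in terms and governs this step, so there is no conflict here. The literal definition does, however, produce an odd sequence. A patient at 165/105 who repeats at 185/92 is stopped by the note, while a patient whose first reading is 185/92 does not meet the definition at all. The same reading gives opposite results depending on when it is taken.
3. Release after medication adjustment. Protocol 7.2 asks that the repeat values not meet the exclusion criteria. If that phrase points to the literal definition, 185/92 releases the patient; if it points to the either-value rule, it does not. The and/or in Protocol 10.2.1 and in footnote 2 can be read as requiring both values to have come down, or only one. This step is ambiguous rather than contradictory.

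On intent, the evidence agrees. The note says either value, and the procedures section and both schedules say DBP and/or SBP. In the same list, criterion 10 uses and/or when it lists ALT, AST and bilirubin, so the drafters used that form where any one abnormal result should exclude.

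Last, the analysis sets. SAP 5.2.1.2 defines the FAS as everyone randomized, and SAP 5.2.1.1 defines the safety population as everyone randomized who took at least one dose. Neither removes patients for entry deviations. SAP 5.2.2 reviews entry deviations against the criteria, but its classification does not change who is analysed.

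**The case against.** The best answer is that the protocol already resolves the reading. The note sits inside the same numbered item, and its wording about values that continue to be at or above threshold presupposes that one high value counted at the first reading too. The trigger for the additional assessment is loose enough to cover a single high value. A sensible investigator who reads the whole item would stop a patient at 185/92. On this view the matter is editorial.

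Much of that stands, and it is why the severity is low. It does not remove the point. It concedes that the sentence defining the exclusion is not the intended rule, and an exclusion criterion should state the rule it means.

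It also limits what may be inferred. A reader might conclude that the protocol sets no systolic ceiling when DBP is below 100, or that a first reading of 185/92 can never lead to a retest. Both follow only if the definition is read without the sentences after it. Those sentences point to either value, and the trigger is unspecific rather than restrictive.

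A further objection is timing. The current amendment is dated 10 May 2017 and the final SAP 22 March 2018, and no last randomization date is given. The documents do not show whether screening was still open, so the practical gain of a prospective change cannot be confirmed from them.

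**Conclusion.** The definition in criterion 7 is wrong as written: it requires both values to be high, while the note, Protocol 10.2.1 and footnote 2 in both schedules show that either should exclude. The release wording after medication adjustment needs clarifying for the same reason. What is at stake is patient safety at entry and uniform eligibility decisions.

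The consequence is small in statistical terms. Nothing changes in power, type I error or the analysis sets. A reader might go on to infer that ineligible patients were enrolled, that sites did apply the rule differently, or that the treatment comparison is biased. The documents support none of these. They contain no blood pressure distribution, no number screened and no record of site decisions, and all randomized patients stay in the FAS whatever their entry status. The number of patients affected cannot be estimated.

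The conclusion rests on one assumption, that the either-value rule is the intended one. Every passage other than the definition supports it, so confidence in the wording conflict is high. Severity is low.

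**What to change.** In Protocol 7.2, criterion 7, and in the matching synopsis item, change the definition to SBP ≥160 mmHg and/or DBP ≥100 mmHg. Add one sentence stating that both values must be below threshold at the reading on which the patient qualifies, including a reading taken after medication adjustment. Use the same release sentence in Protocol 10.2.1, in footnote 2 of Protocol Appendix 1 and in footnote 2 of SAP Appendix 1. With this change 185/92 and 150/105 are excluded, and 165/105 and 150/92 are treated as before.

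SAP 5.2.2 needs no change, because entry deviations do not alter the FAS or the safety population. The cost is one connective in two places, one sentence and its repeats, and slightly more screen failures if screening is still open.

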### **7.3. Patient Lifestyle and Dietary Guidelines**

Each dose of study drug is comprised of 1 tablet from 1 bottle that will be dispensed at each scheduled clinic visit. Study drug should be taken *once a day (once every 24 hours) at approximately the same time every day* and may be taken with or without food. If a patient forgets to take study drug in the morning, it may be taken up to 12 hours later the same day. If study drug has not been ingested by that time, the patient should not take study drug that day and should resume ingestion of study drug the following morning.

Patients will fast for a minimum of 10 hours prior to collection of all laboratory samples.

Patients will be counseled to follow a lipid-lowering diet as per local or regional guidelines and should be encouraged (as able) to participate in a regular exercise program throughout the study.

### **7.4. Investigator/Sponsor Suspension or Termination of Patient Enrollment**

If, in the opinion of the Investigator, the clinical observations in the study suggest that it may be unwise to continue, the Investigator may suspend or terminate the study after consultation with the Sponsor (or designee). A written statement fully documenting the reasons for such a termination will be provided to the Sponsor (or designee) and the Institutional Review Board (IRB) or Independent Ethics Committee (IEC).

The Sponsor has the right to terminate the study or to close a site and remove all study materials from the clinical site. A written statement will be provided to the Investigator, the IRB or IEC, and regulatory authorities, if required.

Possible reasons for termination of the study at a clinical site include, but are not limited to:

[figure not shown]
- Unsatisfactory enrollment with respect to quantity or quality
- Inaccurate or incomplete data collection on a chronic basis
- Falsification of records
- Failure to adhere to the protocol
- Lack of study oversight by the Principal Investigator and/or designee

If any serious or nonserious AEs have occurred at such a clinical site, all documentation relating to the event(s) must be obtained.

## 8. TREATMENT OF PATIENTS

### 8.1. Description of IMP

Table 4: Investigational Medicinal Products

	Investigational Medicinal Product	
Product Name:	ETC-1002	Placebo
Dosage Form:	Film-coated tablets	Film-coated tablets
Unit Dose:	180 mg	Not applicable
Container/Closurea	35- and/or 100-count bottle (depending upon visit) with screw on, non-child proof cap	35- and/or 100-count bottle (depending upon visit) with screw on, non-child proof cap
Route of Administration:	Oral, daily in the morning, with or without food	Oral, daily in the morning, with or without food
Physical Description:		
Manufacturer (Fill/Finish):		

a A 100-day supply of IMP will be included in the 100-count bottle and a 35-day supply of IMP will be included in the 35-count bottle.

Please see Pharmacy Manual for detailed storage requirements and instructions.

### 8.2. Concomitant Medications

Patients will be questioned about their concomitant medication use at each clinic visit. All concomitant medication taken chronically or intermittently during the study must be recorded with indication, total daily dose, and start and stop dates of administration.

The Prior/Concomitant electronic case report form (eCRF) will be used to record medications, herbal remedies, vitamins, other supplements, and over-the-counter medications taken within 3 months prior to screening and during the study.

### 8.2.1. Lipid-Regulating Medications and Supplements

Patients will be required to be on stable lipid-modifying therapy(s), including a maximally tolerated statin for at least 4 weeks prior to screening. Use of fibrates must be stable at least 6 weeks prior to screening. Gemfibrozil, a fibrate, is prohibited. *Patients may not currently be taking or have taken a PCSK9 inhibitor within 4 weeks prior to Screening (Week -2, Visit S1); however, they may be allowed to initiate a PCSK9 inhibitor as adjunctive therapy at Week 24 if the LDL-C threshold criteria have been met as described in Section 11.1.6.3.5.* Stable lipid-modifying therapy(s) includes, but is not limited to, monotherapies or combination therapies containing the compounds below:

#### Statins

- Atorvastatin (Lipitor®, Sortis®)
- Fluvastatin (Lescol®)
- Lovastatin (Mevacor®, AltopenTM)
- Pravastatin (Pravachol®)
- Pitavastatin (Livalo®, Lipostat®)
- Rosuvastatin (Crestor®)
- Simvastatin (Zocor®), with *daily* doses *less than* 40 mg

#### Selective cholesterol and/or bile acid absorption inhibitors

- Cholestyramine/*Colestyramine* (Questran®, Questran Light®, Prevalite®, Locholest®, Locholest® Light)
- Colestipol (Colestid®)
- Colesevelam hydrochloride (Welchol®, Cholestagel®)
- Ezetimibe (Zetia®, Ezetrol®)

#### Fibrates

- Fenofibrate (Antara®, Lofibra®, Tricor®, TriglideTM, Lipantil®, Supralip®)
- Bezafibrate (Bezalip®)
- Ciprofibrate (Modalim®)

**PCSK9 inhibitors** (*allowed as adjunctive therapy beginning at Week 24 [Visit T5]; see Section 11.1.6.3.5*)

- Alirocumab (Praluent®)
- Evolocumab (Repatha®)

#### Other

- Ezetimibe/simvastatin where simvastatin is *less than* 40 mg/day (*Vytorin® 10 mg/10 mg and 10 mg/20 mg, Inegy® 10 mg/20 mg are allowed*)

- Atorvastatin/ezetimibe (Atozet®)

### **8.2.2. Prohibited Medications**

Patients will not have used medications (monotherapies or combination therapies) listed below within 4 weeks prior to screening or use these drugs during the study:

- New or planned dose changes of systemic corticosteroids. Stable doses of systemic corticosteroids at screening are allowed ( $\geq 4$  weeks). Short-term intermittent use ( $< 14$  days) of pulse steroids are allowed.
- Gemfibrozil (Lopid®)
- Cholestin (red yeast rice, also known as monascus purpureus extract)
- Simvastatin (Zocor®), *greater than or equal to 40 mg/day*
- *Ezetimibe/simvastatin where simvastatin doses are greater than or equal to 40 mg/day (Vytorin® 10 mg/40 mg and 10 mg/80 mg per day and Inegy® 10 mg/40 mg and 10 mg/80 mg per day are prohibited)*

*Patients will not have used the medications listed below within 4 weeks prior to screening:*

- Alirocumab (Praluent®)
- Evolocumab (Repatha®)
- *Note: Patients may be allowed to initiate a PCSK9 inhibitor as adjunctive therapy at Week 24 if the LDL-C threshold has been met as described in Section 11.1.6.3.5.*

